### **Safety topic of special interest**

Incidence rate for safety topic of special interest will be provided. The latest project eCRS will be used for reporting.

#### **2.5.1.2 Laboratory data**

Baseline is defined as last assessment (including unscheduled assessments) on or before the first dose day of treatment period.

Descriptive summary statistics for laboratory data (hematology and serum chemistry) will be provided at baseline and post-baseline by test category, parameter, and visit during the treatment period on SAF.

For each parameter, the maximum change from baseline (maximum decrease and maximum increase) will be analyzed analogously.

In addition, shift tables will be provided for all parameters to compare a subject's baseline laboratory evaluation relative to the most extreme laboratory test value within a treatment period. For the shift tables, the normal laboratory ranges will be used to evaluate whether a particular laboratory test value is normal, low, or high (including category "high and low"). These summaries will be presented by laboratory test and treatment group.

The following laboratory parameters will be analyzed with respect to numerical Common Terminology Criteria for Adverse Event (CTCAE) grades (version 5.0), given in [Table 2-3](#): hemoglobin, platelets, white blood cell count, neutrophils, lymphocytes, creatinine, total bilirubin (TBL), gamma-glutamyl transferase (GGT), alanine aminotransferase (ALT), aspartate aminotransferase (AST), alkaline phosphatase (ALP).

The number and percentage of subjects with CTCAE grade newly occurring or worsening after baseline will be presented.

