 Detailed description of physical exam in [Table 8-9](#). Complete physical exam: day 1 of the treatment period. Short physical exam: all other visits.

 UPDD: Urticaria Patient Daily Diary; UAS: Urticaria Activity Score;

 Only performed in women of childbearing potential

 Only performed in women of childbearing potential. In addition to tests during study visits, urine pregnancy tests can be performed at home at Week 24, 32, 36, 44, and 48. Sites must contact subjects to obtain test results. Any positive or undetermined test result must be confirmed by a serum pregnancy test done by central lab.

 Only assess if day 1 is more than 1 week after roll-over date from core study (Week 12 or Week 16)

 Only assess if subjects rollover at Week 16 or if subjects rollover at Week 12 and day 1 of treatment period is more than 1 week after Week 12 of core study

 EoTV (End-of-Treatment Visit) is after completion of the treatment period (Week 52 Visit), or directly after early discontinuation of study treatment (see [Section 9.1](#))

 Only for subjects eligible for extended follow-up

 Phone call visits: after Week 56, all eligible subjects in extended follow-up should be contacted every 4 weeks by phone until Study Completion visit which is a site visit

 SCV (Study Completion Visit) is 4-16 weeks after EoTV:

- all subjects should be followed-up for a minimum of 4 weeks after EoTV
- the extended follow-up of eligible subjects (completion of treatment period and a UAS7≤6 at Week 52) should be stopped after relapse of CSU, initiation of a prohibited therapy (see [Section 6.2.2](#)), decision of the subject or the investigator to stop the follow-up, rolling-over into a post-trial access program (if available), or reaching the maximum follow-up time (16 weeks, Week 68 Visit)

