## **9.2 Study completion and post-study treatment**

Study completion is defined as when the last subject finishes their Study Completion visit, and any repeat assessments associated with this visit have been documented and followed-up appropriately by the Investigator, or in the event of an early study termination decision, the date of that decision.

In the event of an early study termination, all subjects should perform the Week 52 visit (End-of-Treatment visit) as quickly as possible after their last dose and the Week 56 Follow-up visit (4 weeks later).

A post-trial access program (which may be another extension study or a managed access program) for subjects who complete this study is under consideration.

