### **ECGs**

Summary statistics will be provided for ECG parameters by visit during treatment period. Shift table on normal ranges and number and percentage of notable abnormalities will also be summarized.

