### 1.1 Study design

This study is an open-label, single arm, multicenter, long-term safety and tolerability extension study for CSU patients who have participated in CLOU064A2201 or other preceding studies with LOU064 and fulfil the enrollment criteria for the extension study.

The study will consist of three periods: observational period (up to 12 weeks), treatment period (52 weeks), and follow-up period (4-16 weeks).

Approximately 250 patients will enroll into this extension study.

The following study periods will be considered for analysis:

- **Observational period** (Enrollment in observation period to end of observation period (up to Week 12))
- **Treatment period** (Enrollment in treatment period to Week 52 including follow-up visits for patients prematurely discontinued)
- **Entire study period** (Enrollment in treatment period to EoS (End of study) including follow-up visits for all patients)

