### 2.1.1.3 Assessment window for Study Week (eDiary)

The study weeks for assessment completed on eDiary are defined based on the study days starting with Day 1 (Enrollment in observational/treatment period Day).

For completers of treatment period, the study day for eDiary date will be calculated as [Date of Diary] – [Date of Enrollment] + 1 for post-baseline assessment and [Date of Diary] – [Date of Enrollment] for baseline assessment. The analysis Week 1 through Week 51 of the treatment period will be derived based on scheduled visit day as defined in [Table 2-1](#). The analysis Week 52 score will be derived as Day -7 to Day -1 of actual Week 52 study visit day.

During the follow-up period, the study weeks for assessment completed on eDiary are defined based on the study days starting with Day 1 of follow-up period (actual Week 52 visit day). The study day for the eDiary date will be calculated as [Date of Diary] – [Date of Week 52 visit day] + 1. The analysis follow-up Week 1 to Week 16 will be derived based on the actual Week 52 study visit day as defined in [Table 2-1](#).

For early discontinued patients, it is suggested to collect the eDiary data even after the patient discontinued from treatment per “Treatment policy strategy” (this part of data is named as “retrieved drop-out data”). The retrieved drop-out data will be included in the weekly score derivation per assessment window defined in [Table 2-1](#).

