### 2.5.1.3 ECGs

Summary statistics will be provided for ECG parameters by visit/time. Shifts with respect to normal ranges and number and percentage of notable abnormalities will also be summarized.

Triplicates measurements on ECG are scheduled for some visits. For numeric measurements, the mean of the scheduled measurements will be used. For ECG overall interpretation, most common interpretation (normal/abnormal) of the three assessments taken will be used.

PR, QRS, QT, QTcF, and RR intervals will be obtained from 12-lead ECGs for each subject during the study. Frequency tables will be produced for the number and percentage of subjects with notable QT and QTcF intervals and with noteworthy PR, QRS and Heart Rate interval or changes from baseline.

For ECGs, a notable QT and QTcF interval value is defined as:

- QT > 500 msec;
- QTc (Fridericia's) interval > 450 msec (males), QTc (Fridericia's) interval > 460 msec (females);
- QTc (Fridericia's) interval change from baseline > 30 msec, >60 msec;
- PR > 250 msec.

All ECG data will be listed by subject and visit/time for patients experienced and ECG abnormalities.

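### Lab worst-value tables count off-drug follow-up for early stoppers but not for completers, and early End-of-Treatment values fall by default in the Week 52 row of the by-visit safety tables

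*SAP*

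**What the plan says.** **Period.** SAP 1.1 defines the treatment period for analysis as "Enrollment in treatment period to Week 52 including follow-up visits for patients prematurely discontinued". Follow-up visits of all patients belong only to the entire study period, defined in the next item of that list.

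**Labs.** SAP 2.5.1.2 gives descriptive statistics "by test category, parameter, and visit during the treatment period on SAF", then the maximum increase and decrease from baseline in the same manner. Its shift tables compare baseline "relative to the most extreme laboratory test value within a treatment period". The CTCAE tables there and the liver tables in SAP 2.7.3 count abnormalities that arise after baseline; the visible text sets no end date.

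**ECG and vital signs.** SAP 2.5.1.3 says "Summary statistics will be provided for ECG parameters by visit/time", where protocol 12.4.1 has "Summary statistics will be provided for ECG parameters by visit during treatment period". SAP 2.5.1.4 summarises vital signs at every post-baseline visit. Neither SAP section states a period limit.

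**Visits.** In protocol Table 8-1 a single column serves both Day 365 (Week 52) and early termination. Footnote 10 says that this End-of-Treatment visit (EoTV) "is after completion of the treatment period (Week 52 Visit), or directly after early discontinuation of study treatment". Protocol 9.1.1 asks early stoppers to return four weeks later for the Study Completion Visit (SCV), at which Table 8-1 schedules chemistry, hematology, ECG and vital signs.

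**Windows and on-treatment rule.** SAP 2.1.1.3 sets day windows for diary data: "The study weeks for assessment completed on eDiary are defined based on the study days starting with Day 1". SAP 2.1.1.5 treats safety events as on-treatment if they occur before the earlier of last dose + 28 days and the end-of-study visit. The lab, ECG and vital-sign sections do not refer to that rule.

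**The concern.** Protocol 12.4.1 lists laboratory results, ECGs and vital signs among the primary variables. The study is single-arm and tests no hypothesis, so the descriptive tables are themselves the result.

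Two things blur them. First, a worst-value table should describe one kind of observation time for everybody. Here the period is longer for early stoppers by a visit made off drug, so a value that arises or rebounds after stopping counts for them and not for completers. Second, a Week 52 row should describe subjects at about one year. If it also holds values from subjects who stopped at, say, Week 10, it describes a mixture of durations.

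Stopping is not random with respect to these data. Protocol 9.1.1 names platelet, liver, renal and ECG findings among the grounds for discontinuation, so the values affected include some of those that matter most for safety.

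**Working it through.** **Step 1: does the lab rule treat the two groups differently?** Inputs: SAP 1.1, SAP 2.1.1.5, protocol Table 8-1 and protocol 9.1.1. Take EoTV on the day of the last dose and the SCV 28 days later; a later EoTV only moves the SCV further from the last dose.

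| | Early stopper | Completer |
|---|---|---|
| Last dose and EoTV | Day 85 | Day 365 |
| SCV | 85 + 28 = Day 113 | 365 + 28 = Day 393 |
| Before last dose + 28 days (SAP 2.1.1.5)? | No | No |
| In the treatment period (SAP 1.1)? | Yes | No |

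The two visits are equally far from the last dose. The on-treatment rule leaves out both; the treatment period takes in one. The lab shift and maximum-change tables use the treatment period.

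**Step 2: how much could the extra visit add?** The documents give no abnormality rate or discontinuation rate, so this is illustration only. Assume a chance p of an abnormal value at each visit, the same on and off drug, with independent visits. Over k visits, P(any abnormal) = 1 − (1 − p)^k. A subject stopping at Day 85 has k = 3 (Days 29, 57 and EoTV), or 4 with the SCV.

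- p = 1%: 3.0% becomes 3.9%.
- p = 2%: 5.9% becomes 7.8%.
- p = 5%: 14.3% becomes 18.6%.

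A completer at p = 2% has k = 8, giving 14.9%; counting the SCV would make it 16.6%.

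With N treated subjects and a share d stopping at Day 85, the expected number of extra subjects with an abnormal worst value, per parameter, is N × d × p(1 − p)^3. For N = 250:

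- d = 10%, p = 1%: 25 × 0.0097 = 0.2.
- d = 20%, p = 2%: 50 × 0.0188 = 0.9.
- d = 30%, p = 5%: 75 × 0.0429 = 3.2.

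**Step 3: what goes into the Week 52 row?** By-visit tables, one shared visit column and no day windows for these data leave the visit label as the only sorting key in the visible text. Assume that N = 250, that everyone attends EoTV and that stops are spread evenly from Day 1 to Day 365 (mean Day 183). Early values in the row = N × d. Mean day of the row = (1 − d) × 365 + d × 183. A parameter that drifts linearly by 10 units over the year shows as 10(1 − d) + 10 × d × 0.5.

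| Assumed d | Early values of 250 | Mean day | 10-unit drift shows as |
|---|---|---|---|
| 10% | 25 | 347 | 9.5 |
| 20% | 50 | 329 | 9.0 |
| 30% | 75 | 310 | 8.5 |

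Another shape gives another answer: a parameter that shifts early and then stays flat shows almost no dilution, and extreme values at stopping could move the row the other way.

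**The case against.** **The treatment period may be one calendar window.** SAP 1.1 can be read as running to Week 52 for everyone and keeping visits made after stopping, in line with the treatment-policy approach that SAP 2.1.1.3 takes to diary data. An early stopper's SCV usually falls before Week 52. Early stoppers may also still have the lower chance of any abnormal value: 7.8% against 14.9% in Step 2. This shows that the choice could be defended, and that early stoppers need not look worse overall. It does not remove the point: off-drug values still count for one group only, in conflict with the SAP's own on-treatment rule, and no reason is given.

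**Nothing says that early values are tabulated as Week 52.** True. A reader might infer a stated rule, particularly from protocol 9.2, where "all subjects should perform the Week 52 visit (End-of-Treatment visit) as quickly as possible after their last dose". That sentence concerns termination of the whole study by the sponsor. For an individual who stops, protocol 9.1.1 speaks only of the End-of-Treatment visit, and footnote 10 attaches the Week 52 label to completion. What remains is a default created by the shared column and the missing windows.

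**Abnormalities that lead to stopping are not hidden.** Also true. They can appear in the CTCAE and liver tables, in adverse events leading to discontinuation and in the listings, none of which needs a Week 52 label. The treatment-emergent adverse event definition has its own cut-off in SAP 2.5.1.1.

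**Other text might settle it.** SAP 2.1.1.1 names a treatment-free group but does not say which visits belong to it. Text after the lab tables in SAP 2.5.1.2 is blacked out and could not be checked.

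**Conclusion.** The point holds in two parts of different strength.

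1. For lab worst-value tables the asymmetry follows from the stated definitions. Off-drug SCV values enter for early stoppers and not for completers, although an on-schedule SCV lies at or beyond the SAP's own on-treatment limit for both.
2. For by-visit lab, ECG and vital-sign tables, early EoTV values fall in the Week 52 row by default, because the visible text gives no rule that separates them.

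Three stronger readings are not supported:

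- That the Week 52 row mixes on- and off-drug values. Protocol 9.1.1 places EoTV as soon as possible after the last dose, so that row mainly mixes times.
- That the worst-value asymmetry also applies to ECGs and vital signs. SAP 2.5.1.3 and 2.5.1.4 contain no most-extreme-value shift and no period limit; their notable-value counts simply lack a stated cut-off.
- That the figures in Steps 2 and 3 estimate a bias. They rest wholly on assumed rates, even spacing of stops, full attendance and linear drift. Because the documents give no discontinuation rate, the size cannot be computed.

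No hypothesis test or error rate is affected. The change is worth making because these tables serve the primary safety objective.

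**What to change.** **Cut-off.** In SAP 2.5.1.2 and 2.7.3, apply one on-treatment cut-off based on last dose + 28 days (SAP 2.1.1.5) to completers and early stoppers alike. Use it for the lab maximum-change, shift, CTCAE and liver newly-occurring tables, and list or summarise later values separately as follow-up. Use the same cut-off for ECG and vital-sign notable-value counts. State whether the 28th day itself counts, since an on-schedule SCV can fall exactly on it.

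**By-visit tables.** Restrict Week 52 to values in a window around Day 365. Either show early EoTV values in their own row or map them by actual study day to visits at which that assessment is scheduled. For ECG that means no Week 16 row, because Table 8-1 schedules none there and the row would hold only selected subjects. If several values fall in one window, use the one closest to the target day. Give the SCV its own row.

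**Cost.** SAP wording and a little programming, with no new data. The Week 52 n becomes smaller, but it is then the number actually observed at about one year.

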**Table 2-3 CTCAE grades for laboratory parameters to be analyzed**

CTCAE term	Laboratory assessment	Grade 1	Grade 2	Grade 3	Grade 4
Anemia	Hemoglobin (Hgb)	<LLN-10.0 g/dL;	<10.0- 8.0 g/dL;	<8.0 g/dL;	Life-threatening consequences;
Platelet count decreased	Platelet	<LLN-75,000/mm  ;	<75,000-50,000/mm  ;	<50,000-25,000/mm  ;	<25,000/mm  ;
White blood cell decreased	White blood cell	<LLN-3000/mm  ;	<3000-2000/mm  ;	<2000-1000/mm  ;	<1000/mm  ;
Neutrophil count decreased	Neutrophils	<LLN-1500/mm  ;	<1500-1000/mm  ;	<1000-500/mm  ;	<500/mm  ;
Lymphocyte count decreased	lymphocytes	<LLN-800/mm  ;	<800-500/mm  ;	<500-200/mm  ;	<200/mm  ;
INR increased	INR	>1.2 - 1.5; >1 - 1.5 x baseline if on anticoagulation ; monitoring only indicated	>1.5 - 2.5; >1.5 - 2.5 x baseline if on anticoagulation ; dose adjustment indicated	>2.5; >2.5 x baseline if on anticoagulation ; bleeding	-
Creatinine increased	Serum creatinine	>1-1.5 x ULN	>1.5 - 3.0 x baseline; >1.5 - 3.0 x ULN	>3.0 x baseline; >3.0 - 6.0 x ULN	>6.0 x ULN
Blood urea Nitrogen (BUN) increased	Urea	>1- 1.5xULN	>1.5 - 3.0 x baseline; >1.5 - 3.0 x ULN	>3.0 x baseline; >3.0 - 6.0 x ULN	>6.0xULN
Blood bilirubin increased	Total bilirubin (TBL)	>ULN - 1.5 x ULN if baseline was normal; > 1.0 - 1.5 x baseline if	>1.5 - 3.0 x ULN if baseline was normal; >1.5 - 3.0 x baseline if	>3.0 - 10.0 x ULN if baseline was normal; >3.0 - 10.0 x baseline if	>10.0 x ULN if baseline was normal; >10.0 x baseline if

		baseline was abnormal	baseline was abnormal	baseline was abnormal	baseline was abnormal
GGT increased	Gamma-glutamyl transferase (GGT)	>ULN - 2.5 x ULN if baseline was normal; 2.0 - 2.5 x baseline if baseline was abnormal	>2.5 - 5.0 x ULN if baseline was normal; >2.5 - 5.0 x baseline if baseline was abnormal	>5.0 - 20.0 x ULN if baseline was normal; >5.0 - 20.0 x baseline if baseline was abnormal	>20.0 x ULN if baseline was normal; >20.0 x baseline if baseline was abnormal
Alanine aminotransferase increased	Alanine aminotransferase (ALT)	>ULN - 3.0 x ULN if baseline was normal; 1.5 - 3.0 x baseline if baseline was abnormal	>3.0 - 5.0 x ULN if baseline was normal; >3.0 - 5.0 x baseline if baseline was abnormal	>5.0 - 20.0 x ULN if baseline was normal; >5.0 - 20.0 x baseline if baseline was abnormal	>20.0 x ULN if baseline was normal; >20.0 x baseline if baseline was abnormal
Aspartate aminotransferase increased	Aspartate aminotransferase (AST)	>ULN - 3.0 x ULN if baseline was normal; 1.5 - 3.0 x baseline if baseline was abnormal	>3.0 - 5.0 x ULN if baseline was normal; >3.0 - 5.0 x baseline if baseline was abnormal	>5.0 - 20.0 x ULN if baseline was normal; >5.0 - 20.0 x baseline if baseline was abnormal	>20.0 x ULN if baseline was normal; >20.0 x baseline if baseline was abnormal
Alkaline phosphatase increased	Alkaline phosphatase (ALP)	>ULN - 2.5 x ULN if baseline was normal; 2.0 - 2.5 x baseline if baseline was abnormal	>2.5 - 5.0 x ULN if baseline was normal; >2.5 - 5.0 x baseline if baseline was abnormal	>5.0 - 20.0 x ULN if baseline was normal; >5.0 - 20.0 x baseline if baseline was abnormal	>20.0 x ULN if baseline was normal; >20.0 x baseline if baseline was abnormal

ULN: Upper limit of normal range; LLN: Lower limit of normal range.

For laboratory test values below Lower Level of Quantification (LLQ) or above Upper Level of Quantification (ULQ) will be imputed as LLQ or ULQ value, respectively.

Laboratory data will be listed and values outside the normal ranges will be flagged by subject, and visit/time for patients who have experienced any abnormalities.

[REDACTED]

[REDACTED]

[REDACTED]

[REDACTED]

[REDACTED]

[REDACTED]

### 2.5.1.3 ECGs

Summary statistics will be provided for ECG parameters by visit/time. Shifts with respect to normal ranges and number and percentage of notable abnormalities will also be summarized.

Triplicates measurements on ECG are scheduled for some visits. For numeric measurements, the mean of the scheduled measurements will be used. For ECG overall interpretation, most common interpretation (normal/abnormal) of the three assessments taken will be used.

PR, QRS, QT, QTcF, and RR intervals will be obtained from 12-lead ECGs for each subject during the study. Frequency tables will be produced for the number and percentage of subjects with notable QT and QTcF intervals and with noteworthy PR, QRS and Heart Rate interval or changes from baseline.

For ECGs, a notable QT and QTcF interval value is defined as:

- QT > 500 msec;
- QTc (Fridericia's) interval > 450 msec (males), QTc (Fridericia's) interval > 460 msec (females);
- QTc (Fridericia's) interval change from baseline > 30 msec, >60 msec;
- PR > 250 msec.

All ECG data will be listed by subject and visit/time for patients experienced and ECG abnormalities.

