#### **8.4.2      Electrocardiogram (ECG)**

ECGs will be analyzed centrally and performed with ECG machines supplied by the central provider. Standard 12-lead ECGs (single readings) must be recorded after 10 minutes rest in the supine position according to the ECG investigator manual at the timepoints indicated in [Table 8-1](#). The preferred sequence of cardiovascular data collection during study visits is ECG collection first, followed by vital signs, and blood sampling. The Fridericia QT correction formula (QTcF) should be used for clinical decisions.

For any ECGs with treatment emergent abnormalities, two additional ECGs must be performed to confirm the abnormal finding and copies forwarded to the central ECG laboratory for assessment. A monitoring or review process should be in place for clinically significant ECG findings throughout the study and especially at baseline before administration of study treatment.

In the event that a clinically significant ECG abnormality is identified at the site (e.g. severe arrhythmia, conduction abnormality of QTcF > 500 ms or QTcF prolongation > 60 ms), a copy of the assessment is sent to the core laboratory for expedited review if applicable, and the ECG is repeated (and a copy sent to the core laboratory) to confirm the diagnosis. If the subject is hemodynamically compromised, the investigator or a medically qualified person must initiate appropriate safety procedures without delay (for example cardioversion).

Clinically significant abnormalities must be recorded on the eCRF as either medical history/current medical conditions or AEs as appropriate.

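### SAP 2.5.1.3 sets its only 500 ms category on uncorrected QT, so the notable-ECG table cannot count QTcF above 500; its triplicate sentence also contradicts the protocol's single readings

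*SAP*

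**What the plan says.** **Notable ECG categories.** SAP 2.5.1.3 plans frequency tables with these categories:
- uncorrected QT above 500 msec
- QTcF above 450 msec in men or 460 msec in women
- "QTc (Fridericia's) interval change from baseline > 30 msec, >60 msec"
- PR above 250 msec

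The QTcF cut-offs of 450 and 460 are those of protocol Appendix 1 (16.1), which has no 500 msec tier. Protocol 8.4.2 states: "The Fridericia QT correction formula (QTcF) should be used for clinical decisions". Among its examples of a clinically significant abnormality it gives "conduction abnormality of QTcF > 500 ms or QTcF prolongation > 60 ms".

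**Number of readings.** SAP 2.5.1.3 says "Triplicates measurements on ECG are scheduled for some visits" and does not name the visits. Two rules follow: "For numeric measurements, the mean of the scheduled measurements will be used", and, for the overall interpretation, "most common interpretation (normal/abnormal) of the three assessments taken will be used". Protocol 8.4.2 says "Standard 12-lead ECGs (single readings) must be recorded after 10 minutes rest in the supine position" at the Table 8-1 timepoints. Further tracings are triggered, not scheduled: "For any ECGs with treatment emergent abnormalities, two additional ECGs must be performed to confirm the abnormal finding". SAP section 4 declares no change to the protocol's analyses.

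**The concern.** ECGs are among the primary variables (protocol 12.4.1), QT prolongation is a named event of interest (protocol 8.4), and ECG monitoring continues partly because of mild hERG inhibition (protocol 8.4.5). No hypothesis is tested, so descriptive counts are the primary analysis. Protocol 8.4.2 gives two QTcF examples of clinical significance. The SAP tabulates one (a rise above 60 ms) but not the other (a value above 500 ms), and places its 500 ms cut on a quantity that depends on heart rate.

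The triplicate sentence raises a smaller question. An abnormal scheduled ECG plus its two confirmatory repeats makes three tracings. If the majority rule were applied to those three, a scheduled abnormal reading could be summarized as normal.

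**Working it through.** The plan states no figure to reproduce. The check is a comparison of texts plus the Fridericia formula. The documents give no heart-rate distribution, so the rates below are assumptions for illustration.

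**Step 1: can the QT row stand in for QTcF above 500?**
QTcF = QT / RR^(1/3), with RR = 60 / heart rate.
- QTcF when QT = 500: 500 / RR^(1/3)
- QT when QTcF = 500: 500 × RR^(1/3)

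| Heart rate (bpm) | QTcF when QT = 500 | QT when QTcF = 500 |
|---|---|---|
| 50 | 470.5 | 531.3 |
| 55 | 485.7 | 514.7 |
| 60 | 500.0 | 500.0 |
| 70 | 526.4 | 475.0 |
| 80 | 550.3 | 454.3 |
| 100 | 592.8 | 421.7 |

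The cuts agree only at 60 bpm. Above that rate the QT row misses subjects: at 80 bpm it is reached only above QTcF 550. Below it the row over-counts: at 50 bpm a QTcF of 475 gives QT = 475 × 1.2^(1/3) = 504.8 and enters the row. The 50 bpm limit in exclusion criterion 6a applies on day 1 of treatment and does not bound later rates.

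**Step 2: does the row for rises above 60 msec close the gap?**
Take whole milliseconds, and assume the baseline reading is the one that met criterion 6a (below 450 in men, below 460 in women).
- QTcF above 500 means at least 501. A rise of at most 60 then needs a baseline of at least 501 − 60 = 441.
- Baselines for which the row can miss such a value are therefore 441–449 (men) and 441–459 (women).
- The highest values missed are 449 + 60 = 509 and 459 + 60 = 519.
- From a baseline of 440 down, any QTcF above 500 is a rise of at least 61 and reaches the row.

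The documents do not say how many subjects have a baseline in that band.

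**Step 3: do the existing rows together identify the value?**
Two hypothetical men at 80 bpm:
- 445 to 504: rise 59, QT = 504 × 0.75^(1/3) = 457.9
- 421 to 455: rise 34, QT = 455 × 0.75^(1/3) = 413.4

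Both fall in the above-450 and above-30 rows and in no other QT or QTcF row. The table cannot tell them apart.

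**Step 4: what do the replicate rules act on?**
With one scheduled reading the mean is that reading, so no numeric summary changes. The mean rule is limited to scheduled measurements, which leaves triggered repeats out. The interpretation rule carries no such limit of its own. Applied to one abnormal scheduled ECG and two normal repeats, it returns normal, two to one. The ECG row of Table 8-1 carries only footnote 8, which concerns timing after roll-over and sets no number of replicates.

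**The case against.** **The SAP does what the protocol asks.** Protocol 12.4.1 calls for notable abnormalities, Appendix 1 defines notable QTc as above 450 or 460, and the SAP reproduces this and adds change categories. QTcF above 500 appears in 8.4.2 as a site-level trigger for expedited review and a repeat ECG, not as a table category. This stands: a reader might infer that the SAP departs from a prescribed analysis, and it does not.

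**Other outputs may count these subjects.** The SAP plans incidence rates for safety topics of special interest (2.5.1.1) under project criteria not reproduced in the document. It also tabulates adverse events by SMQ and preferred term and those leading to discontinuation; protocol 9.1.1 lists clinically significant ECG abnormalities, with QT prolongation as an example, among events that can require discontinuation. By-visit maxima and the ECG listing would also show extreme values. This stands too: the documents do not support saying that QTcF above 500 goes uncounted in the whole report. The gap is shown for this one table.

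**The gap is narrow.** The row for rises above 60 misses such a value only for baselines in a 9 or 19 msec band. That is correct, but reaching that row does not show that a value exceeded 500, so the count is still unavailable from the table.

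**The triplicate sentence may refer to core-study ECGs.** Footnote 8 of Table 8-1 lets a core-study ECG serve as baseline, and protocol 4.5 describes intensive ECG monitoring in that study. Neither document says those ECGs were triplicate, so this reading is neither shown nor excluded. It does not explain a sentence about scheduled visits in this study.

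**Conclusion.** The point holds and is minor. The notable-ECG table in SAP 2.5.1.3 has no category that counts QTcF above 500, and the QT > 500 row cannot supply it: that row misses cases above 60 bpm and over-counts below. What is missing is a severity count for a primary safety variable in one table, not data. The 60 bpm crossover follows from the Fridericia formula; the other heart rates and the paired subjects are illustrations, and the number of subjects affected is unknown.

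The triplicate sentence contradicts protocol 8.4.2, but the correction is close to clerical. A reader might infer that the planned numeric ECG summaries are wrong. They are not, because the mean of one reading is that reading. Only the overall interpretation could change, and only if the majority rule were applied to confirmatory repeats, which the SAP neither states nor rules out.

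**What to change.** In SAP 2.5.1.3:

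1. Add a QTcF > 500 msec row to the notable-value list and keep all existing rows, including QT > 500.
2. State which ECGs feed the notable-value table. One option is any post-baseline ECG, including unscheduled and confirmatory ones, each assessed individually. Without this the new count is ambiguous, because Table 8-1 allows ECGs at unscheduled visits and protocol 8.4.2 requires repeats.
3. Replace the triplicate sentence, for example with: *Scheduled on-study ECGs are single readings (protocol 8.4.2) and are used for by-visit summaries and the overall interpretation. The mean and most-common-interpretation rules do not apply to triggered confirmatory repeats.* If replicate core-study ECGs used as baseline were meant, say so explicitly.

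The cost is one table row and a few sentences. No new data are needed and no existing row is redefined. Item 2 could shift counts in existing rows if the programs currently use a different set of ECGs, so it should be settled before the tables are run.
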